6.8 Study bread accountability

The study breads will be shipped by delivery courier to the MUMC+. Products will be labelled according to the randomization scheme, see paragraph 7.2. The products will be preserved in the freezer with a temperature of -18°C until needed at the central kitchen of the MUMC+, this freezer is only used to store food products. Participants will consume 2 slices study breads for breakfast and 2 slices for lunch.

7. METHODS

7.1 Study parameters/endpoints

7.1.1 Main study parameter/endpoint

Overall symptom score in the short term (within 8 hours)

The primary outcome is the overall GI symptom score after manipulation of information giving a certain expectation about the bread treatment. Overall (GI) symptom score will be measured using VAS (0 to 100 mm) anchored at the low end (score of 0) with the absence of overalls symptoms and at the other end with extreme of severity of symptoms, the worst it has ever been (score of 100) (see also addendum "F2_Klachtendagboek_WoWstudy_ Versie1.0_05-03-2018"). A relevant change is defined as at least a 15 mm increase in self-reported overall symptoms compared with baseline.

7.1.2 Secondary study parameters/endpoints

- Abdominal pain

- Abdominal discomfort

- Belching

- Bloating

- Flatulence

- Diarrhoea

- Constipation

- Urge to empty bowel

- Fullness

- Nausea

- Tiredness

- Headache

- Foggy Mind

Intestinal symptoms, measured on 100-mm VAS.

(See "F2_Klachtendagboek_WoWstudy_

Versie1.0_05-03-2018")

Extra-intestinal symptoms, measured on 100-mm

VAS. (See "F2_Klachtendagboek_WoWstudy_

Versie1.0 05-03-2018")

- Average stool frequency and consistency (measured by the Bristol Stool Scale)

- Changes in mood measured by PANAS (e.g. interested, alert, excited and distressed, ashamed, nervous).

7.1.3 Tertiary study parameters/endpoints

- Participant characteristics in relation to NCGS (demographics, psychological parameters)

7.2 Randomisation, blinding and treatment allocation

After screening and subsequent inclusion in the study, each participant will be assigned to a unique participant identifier code. Participants will be randomly assigned to one of the following experimental conditions:

- 1. Gluten-free expectation and actually receiving gluten-free oat bread (E-, G-).
- 2. Gluten-free expectation but actually receiving gluten-containing oat bread (E-, G+).
- 3. Gluten-containing expectation but actually receiving gluten-free oat bread (E+, G-).
- 4. Gluten-containing expectation and actually receiving gluten-containing oat bread (E+, G+).

The randomisation lists will be generated by an independent co-worker from the same department as the principal investigator who is not further involved in the study, using a publicly available procedure through the internet (http://randomizer.org). This random number generator performs balanced permutations, resulting in an equal number of participants per treatment order followed. Participants will be randomly allocated to the treatment conditions and there will be a stratification on gender using block randomisation (block sizes of 8). The randomisation scheme will be up to n=90, this to be sure in case of dropouts, to randomize potential (new) participants to a new randomization number.

The investigator has no access to the randomisation list that conceals the intervention code. However, since expectation may play a role in the experience of symptoms, the investigator is unblinded to the expectation arm since the investigator has to inform the participant about allocation to the gluten-free or gluten-containing expectation group. Of course, the investigator is blinded to the actual treatment. The randomisation list will be kept in a sealed envelope by the head of the department (prof. dr. [name]), to reveal the treatment in case of medical emergency. Primary investigators of all participating centres will receive the contact details of prof. dr. [name]. The condition numbers as allocated by the independent colleague, who will carry out the randomisation, are registered by the investigator in the screening and enrolment log. Furthermore, the same co-worker will keep the randomisation lists. The "randomization key" will be provided to the investigator only after all experimental and statistical procedures have been completed.

In general, there should be no need to unblind the allocated product. Unblinding should only be done in those rare cases when a participant suffers from a serious adverse event (SAE) and the investigator or independent physician believes that clinical management depends on whether the participant received gluten-free oat bread or gluten-containing oat bread. In

case of emergencies, the co-worker has been provided with the concealment list and will be able to de-blind.

Since this study focuses on the role of expectation on overall symptoms in people with selfreported gluten sensitivity, we cannot give the complete and correct information about the actual intervention to the study participants in advance. This is part of the design of this study. Participants are however informed in the PIF that they will be randomized to receive gluten-free or gluten-containing bread (paragraph 3.2). Only one single person will be scheduled during a test day, so there is no contact between the participants. At the test day, we will give participants a certain expectation by informing participants that they have been allocated to receive the gluten-free bread or gluten-containing bread. In fact, within each of these arm, half of the participants will then be assigned to the actual treatment. The actual treatment cannot be revealed during the study and is blinded for both the investigator as well as the participant. On completion of the study, participants will be debriefed, but to avoid spread of information and bias in the data, the deception associated with the intervention and expectation as well as the aim of the study will only be disclosed after all participants completed the study. If there are any questions after the debriefing, participants can contact the research team at any time (contact details will be given via the debriefing email/mail).

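### One fixed block size of 8, stated in the protocol, and pack labels showing the expectancy arm make part of the E+/E- sequence foreseeable to staff who see earlier allocations

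*Protocol*

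**What the plan says.** Protocol section 7.2 sets out four conditions (expectancy E+ or E-, crossed with bread G+ or G-). It states that "Participants will be randomly assigned to one of the following experimental conditions" and that "there will be a stratification on gender using block randomisation (block sizes of 8"). No other block size is named, and gender is the only stratification factor.

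The bread is well protected: the investigator has no access to the list that conceals it. Expectancy is different. Section 7.2 says that "the investigator is unblinded to the expectation arm since the investigator has to inform the participant", and that the investigator enters the condition numbers in the screening and enrolment log. It also says: "Only one single person will be scheduled during a test day".

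On timing, section 7.2 places assignment after screening and inclusion, and the study outline in section 3 lists randomisation under the test day. Section 3.2 has the baseline questionnaires completed first and the expectancy arm announced about 15 minutes later.

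On the packs, sections 3.2 and 6.7 say that they bear a label referring to the expectancy arm. Section 6.7 adds a subject code. Section 6.8 says that labelling follows the randomisation scheme and that packs are kept frozen at MUMC+ until needed.

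**The concern.** In this design the investigator must know the expectancy arm at the moment of announcing it. Knowing it beforehand is avoidable. A fixed, known block size lets someone who has seen the earlier allocations work out the end of each block.

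This touches the factor that matters most. The primary comparison in section 2 is E+G- against E-G-, planned with 20 per group (section 4.4), and the outcome is a self-rated VAS (section 7.1.1). If the next arm is known or guessable, the choice of whom to book next can depend on it.

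Section 2 itself hypothesises that people with lower emotional well-being respond more to expectancy. Section 7.3 has PHQ-9, PHQ-15 and GAD-7 completed between screening and test day. Information on susceptibility may therefore exist before the arm is announced, although the protocol does not say whether the person booking sees it. Baseline VAS is not a measure of that susceptibility, so adjusting for it could not be relied on to remove such an imbalance.

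**Working it through.** The protocol gives no figure for predictability, so there is none to reproduce. Its planned total fits its block size: 80/8 = 10 blocks and 80/4 = 20 per condition.

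**Inputs.** Block size 8, gender strata and unmasked expectancy (section 7.2); four conditions in equal ratio (section 7.2); 80 participants (section 4.4); three sites (section 3). Assumed, because the protocol does not say: whether sites share a list, the gender split, and who sees which allocations.

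**1. Block content.** 8/4 = 2 per condition, hence 4 E+ and 4 E-. The number of E+/E- orderings is C(8,4) = 70.

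**2. Forced assignments.** The m-th assignment from the end is forced when the last m all belong to one arm. The probability is 2 × C(8−m, 4)/70.

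- 8th (m = 1): 2 × 35/70 = 100%
- 7th (m = 2): 2 × 15/70 = 43%
- 6th (m = 3): 2 × 5/70 = 14%
- 5th (m = 4): 2 × 1/70 = 3%

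The expected number is 1 + 0.429 + 0.143 + 0.029 = 1.6 per block, and 1.6/8 = 20%.

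**3. Best guess.** Always guess the arm with more places left. With a and b places left, the guess is right with probability max(a, b)/(a + b). Averaged over the 70 orderings, positions 1 to 8 give 0.500, 0.571, 0.571, 0.629, 0.629, 0.714, 0.714 and 1.000. The sum is 5.329, and 5.329/8 = 66.6%.

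**4. Scale.** Over 10 complete blocks, 10 × 1.6 = 16 of 80 assignments are forced and 80 × 0.666 = 53 guesses are right, against 40 by chance. Incomplete last blocks in the two strata lower this slightly: a simulation of 80 participants gives 65.9%.

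**5. Limited sight.** In the same simulation, with three sites drawing at random from one shared list and each site using only its own running count, correct guesses fall to about 53%. This holds whether one gender makes up 50%, 70% or 85%. Someone who sees all sites, or works from a per-site list, stays near 66%.

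**6. Packs.** The label shows the expectancy arm (sections 3.2 and 6.7), the pack carries a subject code (section 6.7), and labelling follows the scheme (section 6.8). If subject codes follow list positions, anyone handling the stock can read the next arm without guessing. The protocol does not state whether they do.

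**7. What varying the block size would change.** Simulated running-count guess rates are 68.0% for sizes 4/8, 66.0% for 4/8/12 and 63.7% for 8/12/16, against 66.6% for fixed 8. The average guess rate barely moves. What disappears is the ability to recognise a block end, and with it the certainty in step 2.

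**The case against.** The strongest reply is that the exposure depends on arrangements the protocol does not describe. It does not say who books test days, so a reader might infer that the unmasked investigator does, but the text does not establish it. With three sites and a shared list, an investigator who sees only local allocations is close to chance. Section 7.2 places assignment after inclusion, so the judgement-based exclusions in section 4.3 come earlier; steering would work mainly through booking order, which participants' availability and the menstruation rule also limit. No bias in mm can be calculated. The usual remedy leaves the average guess rate almost where it was. All of this stands and limits the point. It does not remove it: the block size is in a document that the investigators hold, and nothing in the protocol prevents sight of earlier allocations or of pack labels.

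A reader might also infer that the list cannot give equal arms, since 90/8 = 11.25 and section 7.2 speaks of "resulting in an equal number of participants per treatment order followed". The documents do not support this as a fault. The wording is "The randomisation scheme will be up to n=90, this to be sure in case of dropouts": a ceiling and a reserve. A list of 88 fits under it as 11 complete blocks, and section 4.4 caps inclusion at 84. Incomplete last blocks in the two strata can leave a gap of up to 4 between arms in simulation. With the protocol's 15 mm and 12.8 mm, t-test power is 95.1% at 20/20 and 94.9% at 18/22, a loss of 0.2 points. Nor can one say that a gender list would run out, because no split of the list is given.

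**Conclusion.** The point holds as a weakness in concealing the upcoming expectancy arm. For a person who sees every earlier allocation in a stratum, 20% of expectancy assignments are certain and about 67% guessable. For a person limited to one of three sites sharing a list, the guess rate is about 53%. The pack labels may make the arm readable outright, if codes follow list order.

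These figures rest on complete blocks of 8 in equal ratio and on the stated degree of sight; the protocol settles neither who sees what nor whether the list is shared. The documents do not support the stronger readings that the block size is public, that the person booking participants is known to be unmasked, or that selection has biased the primary comparison. The point is worth correcting because the repair is cheap and the affected factor is the primary one.

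**What to change.** For participants not yet allocated, amend sections 3.2, 6.7, 6.8 and 7.2 as follows.

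- **List.** Use a separate list per gender stratum in complete blocks of randomly varying size, each a multiple of four. The independent co-worker holds the sizes, and they are removed from documents that recruiting staff hold. State whether the list is shared across sites or kept per site.
- **Packs.** Put only a neutral code on the pack, with no expectancy arm and no code that reveals list position.
- **Release.** Disclose the expectancy arm and the matching pack code only after the test-day baseline questionnaires are complete, by sealed envelope or electronic release.

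The three parts belong together: withholding the arm until after baseline achieves little while the pack label shows it. The gain is that forced assignments can no longer be recognised with certainty. The amendment should not claim more, since the running-count guess rate stays near 66%.

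The cost is a new list, relabelled packs, a release procedure that works on the test morning at every site, and slightly looser balance at the end of the list.

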2. OBJECTIVES

Primary Objective:

In this randomized, double-blind, controlled study, we aim to investigate the effects of consumer expectancy, related to either gluten-containing or gluten-free oat bread on short-term (within 8 hours) overall GI symptoms in individuals with NCGS.

Hypothesis:

We hypothesize that expected gluten intake via bread consumption (as influenced by verbal information), but not the actual gluten intake increases subjective overall GI symptom score in individuals with NCGS. (see Figure 1, comparison E+G- vs. E-G-).

Expectation Intervention

[figure not shown]

Figure 1. Overview of group comparison related to the primary objective (*i.e.* comparing E-G- vs. E+G- groups). (E- = Expectancy of getting gluten-free bread, E+ = Expectancy of getting gluten-containing bread, G + = actual gluten-containing bread, G- = actual gluten-free bread).

Secondary Objective(s):

 To investigate the effects of the actual intake of gluten on overall symptoms in individuals with NCGS.

Hypothesis:

We hypothesize that expected bread consumption (E+ or E-) (as influenced by verbal information), but not the actual bread composition (G+ or G-) affects subjective GI and extra-intestinal symptoms in individuals with NCGS.

- To investigate the effects of expected gluten intake and actual gluten intake on individual GI and extra-intestinal symptoms in individuals with NCGS.

Hypothesis:

We hypothesise that in participants who expect to receive gluten-containing bread, there will be an increase in GI and extra-intestinal symptoms regardless of the actual bread composition (G+ or G-) in individuals with NCGS.

- To study the impact of emotional well-being on overall, intestinal and extra-intestinal symptoms after expected or actual gluten intake in individuals with NCGS.

Hypothesis:

We hypothesize that individuals with decreased emotional well-being (as measured by PHQ-9, PHQ-15 and GAD-7) are more vulnerable to expectation in relation to gluten intake (as influenced by verbal information) leading to more symptoms.

- To investigate the effects of expectation and/or actual intervention on mood (affective) changes in individuals with NCGS.

Hypothesis:

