3.2 Test day (Day 1)

On the test day, upon arrival in MUMC+, Amsterdam UMC or WUR, the participants will be informed by the researcher(s) that they have been allocated to a specific group (*i.e.* E+ or E-). They will then receive either gluten-containing (G+) or gluten-free (G-) oat bread. The participant and the investigator will both be blind to the actual study intervention the participant will receive, *i.e.* the gluten-containing (G+) or gluten-free bread (G-) within each of the expectancy groups (See Figure 2).

This randomization results in 4 groups:

Group 1: Participants with the expectation of receiving gluten-free bread but actually receiving gluten-containing bread during the test day (E-, G+).

Group 2: Participants with the expectation of receiving gluten-free bread and actually receiving gluten-free bread during the test day (E-, G-).

Group 3: Participants with the expectation of receiving gluten-containing bread and actually receiving gluten-containing bread during the test day (E+, G+).

Group 4: Participants with the expectation of receiving gluten-containing bread but actually receiving gluten-free bread during the test day (E+, G-).

During the test day, participants are asked to come to the MUMC+, Amsterdam UMC or WUR in a fasted state at 8.00AM. Before the participants are informed about which group they are assigned to, they will first have to fill in the symptom questionnaire and the positive and negative affective scale (PANAS) as baseline measurements. Then (± 8.15 AM) they will be informed that they have been allocated to the gluten-containing or gluten–free groups (i.e. creating expectancy, E- or E+) and at 8.30AM they have to consume 2 slices of study bread for breakfast and at 12.30PM a further 2 slices for lunch. All slices can be prepared with margarine plus cooked ham, or cheese, or marmalade (one standardised portion of one topping per slice, all gluten-free). Furthermore, they will be allowed to drink coffee, tea or water (ad libitum) during the test day. Other foods or drinks are not permitted during the test day until 4.30PM. During the test day, the participants are free to do what they want to (watching TV, reading, working, possibly take a walk), provided that they complete the questionnaires every hour.

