5.2 Use of co-intervention (if applicable)

Volunteers reporting a gluten-free or gluten-restricting diet should have been on this for at least one week prior to the study and continue with this throughout the study. To minimalize the influence of altered food and beverage intake on outcome parameters during the study period, the test day will take place at the MUMC+, Amsterdam UMC or WUR in a controlled setting under supervision of the researcher. If part of the test day is carried out outside these study sites, the participants will be given clear instructions on the (un)allowed intake and will be asked to record their beverage intake during the day. Subsequently, we will ask participants to maintain their dietary habits (or the gluten-free/gluten-restricted diet they started prior to the study) as much as possible during the follow-up period. There will be no further dietary restrictions, apart from the test day. During the test day, the participants are free to do what they want to (watching TV, reading, working, possibly take a walk), provided they complete the questionnaires every hour.

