5.3 Escape medication (if applicable)

We do not expect that the use of escape medication will be necessary. However, participants are permitted to use paracetamol if necessary. The use of nonsteroidal anti-inflammatory drugs (NSAIDs) and opioids are not allowed during the test day. The number of tablets, dose, and the reason for the medication use have to be reported in the electronic diary. If paracetamol does not work adequately and participants experience intolerable symptoms during the study, the involved gastroenterologists in this study ([name]) will advise on whether or not to stop the intervention. In that case, VAS-scores for the remaining questionnaires were replenished using the highest VAS-score achieved thus far.

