8.2 AEs, SAEs and SUSARs

8.2.1 Adverse events (AEs)

Adverse events are defined as any undesirable experience occurring to a subject during the study, whether or not considered related to the food intervention (*i.e.* study breads). All adverse events reported spontaneously by the participants or observed by the investigator or his staff will be recorded.

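### The trial is called double-blind without qualification, but the blind covers bread type only; expectancy, the sole difference in the primary contrast, is known to the investigator who announces it

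*Protocol*

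**What the plan says.** The label is unqualified in four places: the summary (study design), section 1, section 2 and section 3. In section 2 it stands in the sentence that states the primary objective: "In this randomized, double-blind, controlled study, we aim to investigate the effects of consumer expectancy". The figure legend there gives the primary comparison as "comparing E-G- vs. E+G- groups".

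The blind itself is defined more narrowly. Section 3.2 says: "The participant and the investigator will both be blind to the actual study intervention the participant will receive". Section 7.2 repeats that the concealed item is the bread, and says of the other factor that "the investigator is unblinded to the expectation arm since the investigator has to inform the participant". Sections 3.2 and 6.7 add that the frozen bread packages carry a label referring to the expectancy arm.

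On conduct, section 5.2 places the test day "in a controlled setting under supervision of the researcher", though section 3.2 lets part of it take place at home or at work. Under section 5.3, if paracetamol is not enough and symptoms are intolerable, the study gastroenterologists "will advise on whether or not to stop the intervention". In that case the remaining VAS scores take the participant's highest score so far. Section 7.5 gives a last-observation-carried-forward rule for participants who withdraw on the test day because of intolerable symptoms.

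**The concern.** A reader of the primary objective will take double-blind to describe the comparison in that objective. It does not. The two groups compared receive the same bread and differ only in what the investigator tells them, and the investigator knows which message was given.

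This matters more here than in most trials because the verbal message is the intervention. If staff deliver it with different emphasis in the two arms, or afterwards ask more about symptoms in E+, the result is more symptom reporting in E+. That is exactly what a nocebo effect looks like, and no analysis can separate the two afterwards. The safeguards therefore have to lie in conduct, and the protocol fixes none for this factor: no standard wording and no limit on symptom talk after the announcement. Without a qualifier, the report could present the primary finding as double-blind evidence.

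**Working it through.** No arithmetic applies. The check sets the statements side by side, factor by factor.

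| | Bread (G+/G-) | Expectancy (E+/E-) |
|---|---|---|
| Participant | blind (3.2, 7.2) | told the arm, by design (3.2) |
| Investigator | blind (3.2, 7.2) | knows the arm (7.2) |
| Package label | concealed (3.2, 6.7) | label refers to the arm (3.2, 6.7) |
| Those advising on stopping | no statement specific to them | not stated (5.3) |
| Differs in E+G- vs E-G-? | no | yes (2) |

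1. The masked factor is constant in the primary contrast, and the factor that varies there is open to the investigator. The same holds for the Expectancy factor in the section 9.1 model. The Gluten factor is the one that is double-blind.

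2. What remains for the primary contrast:
   - Bread type is concealed from the messenger, who cannot know that the message to an E+G- participant is false. This protects the delivery of that message.
   - The primary VAS is completed by the participant in an electronic diary (3.2, 7.1.1), not scored by staff.
   - The deception and the aim are disclosed only after all participants have finished (3.4, 7.2).

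   Staff knowledge can therefore act on the score only indirectly, by influencing what the participant feels or reports.

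3. Conduct after the announcement. The researchers announce the arm (3.2), one participant is scheduled per test day (7.2), and the researcher supervises the on-site part (5.2). The protocol gives no fixed text for the announcement. It requires a check for serious adverse events (3.2) but sets no boundary on other questions about symptoms.

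4. Stopping. Advice to stop under section 5.3 leads to a highest-score fill-in of the remaining questionnaires. If the adviser knew the arm and advised stopping more readily in E+, E+ scores would rise through the fill-in. Whether the adviser knows the arm is not stated.

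5. Two fill-in rules. Section 5.3 uses the highest score so far for the remaining questionnaires. Section 7.5 uses the last score, worded for the remaining days, after withdrawal for intolerable symptoms. The highest score so far can never be below the last, so the two agree only when the last score is also the highest. A participant who stops on the test day because of intolerable symptoms could fall under either.

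**The case against.** The strongest reply is that nothing is hidden. Sections 3.2 and 7.2 say plainly what is blinded and that the investigator knows the expectancy arm, and why. Someone must deliver the message and the participant must hear it, so full masking of expectancy is impossible. All of this stands. The fault is the unqualified label in the summary and in sections 1, 2 and 3, together with the lack of a standard message; section 7.2 itself is correct.

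It can also be said that supervision is meant to control food and drink, that participants are otherwise free during the day, and that a script is working-instruction detail. The first two points are fair and limit the exposure. The third is less convincing where the spoken message is the treatment under test.

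A reader might go further than the documents allow in three ways.

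- That the primary contrast has no protection. It does: concealed bread type, self-rating, and undisclosed aim and deception.
- That readier recording of adverse events in E+ would inflate the primary result. Adverse events are not listed among the endpoints in section 7.1, and recording them does not change a self-rated VAS.
- That the gastroenterologists know the arm. The protocol is silent; it does not say they know it, only fails to say they do not. The route is also narrow: it needs intolerable symptoms after paracetamol, section 12.1 lets participants stop on their own, and section 7.5 expects no dropouts.

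**Conclusion.** The point holds in a limited form. For the factor that defines the primary contrast, the trial lacks the double-blind property that the primary objective claims. The protocol describes no standard announcement and no limit on symptom talk that would reduce the resulting bias route.

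That route is indirect, and its size is unknown. The documents contain nothing that links staff knowledge to a VAS shift, so any shift in millimetres, or any false-positive rate computed from one, would be an assumption rather than a finding. The conclusion rests on the protocol's own account of who knows what. It does not assume that bias will occur. The stopping route is conditional on the advisers knowing the arm, which the protocol leaves open. The mismatch between the fill-in rules in sections 5.3 and 7.5 stands whether or not they do.

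**What to change.** - In the summary and sections 1, 2 and 3, replace the bare label with a statement per factor: double-blind for bread type; expectancy arm known to the participant and to the investigator who announces it. Section 7.2 already says this. Carry the same limit into the conclusions on the primary contrast.
- Specify one fixed announcement script, identical in both arms except for the arm named.
- Have staff ask about symptoms during the test day only through the electronic forms, apart from the safety check that section 3.2 already requires.
- State whether those who advise on stopping under section 5.3 know the expectancy arm, because that advice triggers a fill-in of the primary VAS.
- Reconcile the fill-in rules of sections 5.3 and 7.5, so that each way of stopping or withdrawing falls under one rule.

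The cost is wording changes, a short script and a staff instruction. The sample size, visits and measurements stay as they are, and these steps call for no extra staff.
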